9.4.2 ANALYSIS OF THE PRIMARY EFFICACY ENDPOINT(S)

- The primary outcome of interest is return to dance (binary).
- The proportion of subjects in each group that returned to dance will be evaluated with Pearson's chi-square or Fisher's exact test depending on the distribution of outcomes. If there is fewer than 10 subjects in any group (control that returned to dance, control that did not return to dance, experimental group that returned to dance, experimental group that did not return to dance), Fisher's exact test will be used.
- Odds ratios will be calculated and presented for significant findings.
- Subjects will be excluded if they are missing data related to our primary outcome of interest.

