6 STUDY INTERVENTION

6.1 STUDY INTERVENTION(S) ADMINISTRATION

6.1.1 STUDY INTERVENTION DESCRIPTION

The study intervention will be mental health exercises via the SuperBetter app for dancers participating in PT rehab for foot or ankle injuries. The control will be PT rehab only, without implementation of the SuperBetter app.

Subjects who enroll and are randomized into the treatment arm will be assisted in clinic to log into the app SuperBetter. They will be added to the group run by the “host”/study staff. The SuperBetter app offers a daily exercise on a schedule that will be managed by the “host” or study staff. Subject will complete 1 full activity per day. This activity will not exceed 15 minutes in total including app boot-up, but the full activity itself will not exceed 10. These activities ask participants to practice different exercises that might be found in Cognitive Behavioral Therapy, such as mindfulness. They are framed like a game for engagement, where the subject can “get a power up” when they take 30 seconds to breathe deeply and think of 3 loved ones, as an example. 1 full daily activity is constituted by 4 to 6 very brief activities similar to the previously described.

Both groups will undergo physical exams at their normally scheduled orthopedic appointments at baseline, 8 weeks, 3 months, 6 months, 12 months, 18 months, and 24 months where presence/absence of reinjury, return to dance, adherence to PT and/or the SuperBetter app, type(s) of dance, and hours of dance per week will be assessed. Both groups will be asked to complete the PROMIS, SCS, and FAAM at baseline, 3-, 6-, 12-, 18-, and 24 months.

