6.3 MEASURES TO MINIMIZE BIAS: RANDOMIZATION AND BLINDING

Patients who meet inclusion criteria at this single site will be offered enrollment in this RCT. Enrolled patients will be randomized into one of 2 groups. It will be true randomization without patient preference but will not be blinded. There are no sub-studies or stratifications to be performed within this group.

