9 STATISTICAL CONSIDERATIONS

9.1 STATISTICAL HYPOTHESES

- Primary Efficacy Endpoint(s):
 - Null Hypothesis (H_0): There will be no difference in self compassion scores to return to unrestricted dance at 3 months between the mental health app group and control group.
 - Alternative Hypothesis (H_1): Self compassion and return to unrestricted dance is expected to be improved in the mental health app treatment group compared to control group.
 - Type of Comparison: Superiority
 - Time Point: 12 months
 - Analysis Method: Logistic regression or Fisher's exact test depending on data distribution.
- Secondary Efficacy Endpoint(s):
 - Change in Self-Compassion Scale scores over time (repeated measures ANOVA or nonparametric equivalent) in experimental group compared to control group
 - Association of self-compassion with FAAM and PROMIS scores (correlation/regression)
 - Time to initial return to dance (Kaplan-Meier with log-rank test or Cox regression)
 - Reinjury incidence (descriptive comparison by self-compassion group)

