9.2 SAMPLE SIZE DETERMINATION

Planned Sample Size and Feasibility

The total number of participants planned for enrollment is 50, which includes a buffer to account for expected attrition.

Outcome Measure Used for Sample Size Calculations

Return to unrestricted dance participation at 12 months, a binary (yes/no) outcome.

Test Statistic

A Fisher's exact test will be used to compare the proportion of participants who return to unrestricted dance between experimental and control groups (dichotomized by a median split or similar method).

Statistical Hypotheses

Null Hypothesis (H_0): There will be no difference in self compassion scores to return to unrestricted dance at 3 months between the mental health app group and control group.

Alternative Hypothesis (H_1): Self compassion and return to unrestricted dance is expected to be improved in the mental health app treatment group compared to control group.

Assumptions for Sample Size Calculation

- Alpha (Type I error rate): 0.05 (two-tailed)
- Power (1 - Beta): 0.80 (80%)
- Effect Size: Odds Ratio (OR) = 5.0
- Expected Proportions:
 - Control group: 60% expected to return to dance
 - Experimental: 95% expected to return to dance
- These assumptions are informed by preliminary data and theoretical rationale suggesting that higher self-compassion is strongly associated with better emotional regulation, adherence to rehabilitation, and psychological resilience—all of which plausibly contribute to better recovery outcomes in dancers (Zarzycki et al., Gennarelli et al., Christino et al.).

Statistical Method and Software

- Sample size was calculated using:
 - Validated using G*Power 3.1 (Faul et al. 2007)
- Using these assumptions, the required sample size is:
 - 38 participants total (19 per group) to detect an OR of 5.0 with 80% power at $\alpha = 0.05$.
- Missing data on the primary endpoint (i.e., return to dance status at 12 months) will be minimized through close follow-up and contact strategies. If missing data occur, analyses will proceed using available-case analysis and sensitivity analyses will be conducted as described in Sections 9.4.2 and 9.4.3.
- Interim Analyses
 - No formal interim analyses are planned due to the small sample size and short duration of primary outcome measurement. Therefore, no statistical correction (e.g., O'Brien-Fleming or Pocock boundaries) is required.
- Sensitivity and Robustness Checks

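### The primary analysis is an unadjusted two-by-two test with an odds ratio shown only if significant, while section 9.1 also allows logistic regression with no covariate named, although baseline FAAM is collected

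*Protocol*

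**What the plan says.** Four parts of the protocol bear on this.

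- **Analysis, section 9.4.2.** "The proportion of subjects in each group that returned to dance will be evaluated with Pearson's chi-square or Fisher's exact test", with Fisher's test used when any of the four cells is below 10. On the effect estimate: "Odds ratios will be calculated and presented for significant findings".
- **Hypotheses, section 9.1.** The method for the primary endpoint is given as "Logistic regression or Fisher's exact test depending on data distribution". No covariate is named here or anywhere else for this endpoint.
- **Sample size, section 9.2.** "A Fisher's exact test will be used to compare the proportion of participants who return to unrestricted dance". On numbers: "The total number of participants planned for enrollment is 50, which includes a buffer to account for expected attrition". The calculated requirement is 38, or 19 per group.
- **Design and data.** Section 6.3: "There are no sub-studies or stratifications to be performed within this group". Section 6.1.1: "Both groups will be asked to complete the PROMIS, SCS, and FAAM at baseline, 3-, 6-, 12-, 18-, and 24 months".

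Section 9.4.5 compares age, dance hours and physical therapy exposure between arms. FAAM, PROMIS and SCS are not in that list.

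**The concern.** In a small trial without stratification, the arms can differ by chance in how well participants function at entry. If baseline function predicts return to dance, such a difference moves the unadjusted odds ratio in that trial, up or down. The protocol collects a baseline function score but gives it no role in the primary analysis, and the listed baseline comparisons would not show an imbalance in it.

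Two features of the text add to this. Section 9.1 leaves a regression model open without saying what goes into it or exactly when it would replace the test in 9.4.2, and the trial is not blinded. Section 9.4.2 withholds the odds ratio when the result is not significant, so an effect masked by imbalance would leave no estimate to examine. At stake is how the single reported effect can be interpreted, and whether its model was fixed in advance.

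**Working it through.** **Inputs from the protocol.** Planned enrolment 50, taken as 25 per arm. Required 19 per group. Two-sided alpha 0.05. Return rates 60% and 95%.

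**Assumed input.** The protocol gives no link between baseline FAAM and return to dance. Odds ratios per SD of 1 (no link), 2 and 3 are used as a range.

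**1. The protocol's own figure.** The unpooled normal formula gives n = (1.960 + 0.842)² × (0.60×0.40 + 0.95×0.05) / 0.35² = 7.85 × 0.2875 / 0.1225 = 18.4, so 19 per group. The stated 38 is reproduced. The range of 19 to 25 per arm is used below because 9.4.2 drops participants without the primary outcome.

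**2. Which test would apply.** At the design rates the app arm expects 25 × 0.05 = 1.25 non-returners. That is far below 10, so the rule in 9.4.2 leads to Fisher's test, in line with 9.2. Section 9.1 is the one that differs.

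**3. Validity of the unadjusted test.** Exact enumeration of two-sided Fisher at 25 per arm gives type I error of 2.95% (60% return in both arms) and 2.20% (77.5% in both). In simulation it stayed at 2-3% whether or not the baseline score was prognostic.

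**4. How often chance imbalance occurs.** The standardized difference in one baseline score has SD √(2/n).

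| Per arm | SD | P(difference > 0.5 SD, either way) | Favouring the app |
|---|---|---|---|
| 25 | 0.283 | 7.7% | 3.9% |
| 19 | 0.324 | 12.3% | 6.2% |

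The last column is half of the one before it.

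**5. What it does to the odds ratio.** In 3,000 simulated trials per scenario at 25 per arm, the unadjusted log odds ratio was regressed on the imbalance.

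- Odds ratio 1 per SD: slope about 0, so no shift.
- Odds ratio 2 per SD: slope 0.57 to 0.66. At 0.5 SD the factor is exp(0.29) to exp(0.33), about 1.35.
- Odds ratio 3 per SD: slope 0.84 to 0.91. At 0.5 SD the factor is exp(0.42) to exp(0.46), about 1.55.

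An imbalance the other way divides by the same factor.

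**6. Whether one covariate can be supported.** Expected non-returners are 25 × (0.40 + 0.05) = 11.25, or 19 × 0.45 = 8.55. That allows about one covariate. An app arm of 25 has no non-returner with probability 0.95²⁵ = 28%, and ordinary logistic regression then has no finite treatment estimate. The ordinary adjusted likelihood-ratio test ran at 5.6-6.8% type I error. A Firth-penalised model with one covariate ran at about 3.6-5.2% at both 19 and 25 per arm.

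**7. Power.** For logistic likelihood-ratio tests at 60% versus 95%, unadjusted against adjusted power was 0.91 and 0.91 (odds ratio 1 per SD), 0.91 and 0.92 (odds ratio 2), and 0.90 and 0.94 (odds ratio 3). With the Firth model the covariate changes power by about -3 to +4 points.

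**The case against.** The strongest case against is that nothing here is an error. Randomization makes the unadjusted comparison valid, and its error rate already allows for chance imbalance. A supportive model with a named covariate is routine content for a statistical analysis plan, which may exist and is not shown. The prognostic strength of FAAM is assumed. With 9 to 11 non-returners, a regression could be unstable.

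Much of this stands. A reader might infer that the unadjusted test inflates false positives, but its type I error is 2-3%. A reader might take the 7.7% as the chance of a spurious benefit, but half of those imbalances favour control and would hide an effect. In addition, an imbalance above 0.5 SD favouring the app together with a significant Fisher result for the app occurred in only 0.15-0.37% of simulated null trials, with log-odds of 0.7 to 1.2 per SD assumed. A reader might also expect adjustment to raise power materially. The covariate adds little, and nothing at all to a decision that stays with the unadjusted test.

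Two parts do not stand. The instability argument applies to ordinary logistic regression or several covariates, not to one covariate with a Firth penalty. And the point does not depend on details left to a later plan: the protocol itself gives differing primary methods in 9.1 and in 9.2 and 9.4.2, and itself makes reporting of the odds ratio depend on significance.

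**Conclusion.** The point holds as a minor one. The decision test is sound and need not change. What is poorly fixed is the estimate: it is unadjusted in an unstratified trial of about 50, shown only when significant, and accompanied in 9.1 by an unspecified regression option.

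The size depends on two things. The frequency of imbalance (7.7% at 25 per arm, 12.3% at 19, for any one score) follows from equal arms and normal theory. The consequence (a factor of about 1.35 to 1.55 at 0.5 SD, in either direction) rests on an assumed odds ratio of 2 to 3 per SD of FAAM. With no prognostic link it is zero. The protocol does not say that covariates will be chosen after seeing the data. It only fails to rule this out.

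**What to change.** In sections 9.1, 9.2 and 9.4.2, name the same single unadjusted test for the decision, with Fisher's exact test the natural choice at the design rates. Then add one supportive estimate: Firth-penalised logistic regression of return to dance on arm and baseline FAAM, at the primary time point. State which FAAM score is used and how a missing baseline value is handled. Report its odds ratio and confidence interval whatever the p value, and remove the restriction to significant findings.

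The cost is a few sentences and one extra model, with no change to sample size, data collection or the decision test. There are small downsides. One covariate must be chosen in advance. The adjusted odds ratio is conditional on FAAM and so differs in meaning from the unadjusted one. A few baseline FAAM values may be missing, because sections 2.3.1 and 8.2 let participants skip items. If FAAM is not prognostic, nothing is gained.

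### Sections 9.1, 9.2 and 9.4.2 give three primary-test rules; in effect they amount to a conservative Fisher test, and naming one exact unconditional test would recover some power at the same alpha

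*Protocol*

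**What the plan says.** The primary outcome is binary: return to unrestricted dance, by arm. Three sections of the protocol say how it will be tested, and they differ.

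- **Section 9.1** offers logistic regression or Fisher's, "exact test depending on data distribution".
- **Section 9.2** names one test for the sample size: a Fisher's "exact test will be used to compare the proportion of participants who return to unrestricted dance between experimental and control groups".
- **Section 9.4.2** allows Pearson's chi-square or Fisher's test. "If there is fewer than 10 subjects in any group", meaning any of the four arm-by-outcome cells, Fisher is used.

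Section 9.2 sets a two-sided alpha of 0.05 and 80% power. Its planned rates are "Control group: 60% expected to return to dance" and "Experimental: 95% expected to return to dance". It requires 38 participants (19 per group) and plans to enrol 50. Section 9.4.2 excludes participants with a missing primary outcome, so the analysed number may fall anywhere below 50. Section 6.3 describes no stratification and no blocking, so the arms need not be equal.

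**The concern.** The trial has one primary comparison and few participants. Two things are at stake.

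**Specification.** Logistic regression, Pearson and Fisher can give different p-values on the same table. Section 9.1 lets the choice depend on the data without saying how. In an unblinded trial the test should be fixed before outcomes are known.

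**Efficiency.** Fisher's test conditions on both margins. In small tables this makes its real type I error well below the nominal level. If the cell-count rule always leads to Fisher's decision, the plan leaves alpha unused, and therefore loses power, without gaining validity.

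**Working it through.** **Inputs.** From Section 9.2: two-sided alpha 0.05, power 80%, 60% versus 95%, 19 per group required, 50 enrolled, and the alternative rates 60% versus 90% and 60% versus 85% from its sensitivity table. Assumptions: 1:1 allocation (implied by 19 per group), and analysed totals from 38 to 50, because no attrition rate is given. Splits below are control/experimental.

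**Step 1: the plan's own figure.** The arcsine formula gives h = 2·asin√0.95 − 2·asin√0.60 = 2.6906 − 1.7722 = 0.9184. Then n = 2(1.960 + 0.8416)²/h² = 15.70/0.8435 = 18.6, so 19 per group. The plan's 19 is reproduced, but by a normal-approximation formula and not by the Fisher test that Section 9.2 names.

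**Step 2: does the switch change a decision?** All four cells can reach 10 only if each arm has at least 20, so below that Fisher is certain.
- At 25 per arm and 60/95, the chance that all four cells reach 10 is about 9 × 10⁻⁸.
- At 25 per arm with no effect, Pearson is selected 31.6% of the time at 60/60 and 59.4% at 50/50.
- When Pearson is selected at 25 per arm, the most extreme table is 15 versus 10. With pooled rate 0.5, z = 0.20/√(0.25 × 2/25) = 0.20/0.1414 = 1.41, so p = 0.16. It cannot reject.

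In all splits checked (even totals from 38 to 50, each arm up to 6 from equal), the rule rejects exactly when Fisher does.

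**Step 3: size and power.** Every 2×2 table is enumerated and weighted by the two binomials. Size is the maximum rejection probability over the common rate. Boschloo uses the two-sided Fisher p-value as its statistic and sets the cut-off so that this maximum is at most 0.05. The cut-off is 0.0897 at 19 per arm and 0.0792 at 25. Because these exceed 0.05, Boschloo rejects whenever Fisher does.

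| Arms | Fisher power, 60/95 | Boschloo power, 60/95 | Gain (points) |
|---|---|---|---|
| 19/19 | 68.3% | 77.7% | 9.5 |
| 22/22 | 77.3% | 85.4% | 8.1 |
| 23/23 | 79.8% | 83.4% | 3.5 |
| 24/24 | 82.1% | 85.5% | 3.4 |
| 25/25 | 82.2% | 87.5% | 5.3 |
| 18/20 | 74.5% | 78.1% | 3.6 |
| 21/22 | 83.1% | 83.4% | 0.3 |
| 24/26 | 88.0% | 88.5% | 0.5 |
| 26/24 | 83.3% | 87.8% | 4.6 |

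Gains are taken before rounding.

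- **Average over simple-randomisation splits at 60/95:** N = 38, 69.9% to 76.8% (+6.9); N = 44, 78.9% to 83.3% (+4.4); N = 50, 84.5% to 88.3% (+3.8).
- **Smaller effects in the Section 9.2 table:** at 60/90, +11.9 (19/19) and +9.9 (25/25, 59.1% to 69.0%). At 60/85, +10.2 (19/19) and +11.0 (25/25, 38.3% to 49.4%).
- **Maximum size over the tabulated splits and the others checked from 18 to 27 per arm:** Fisher 2.3 to 3.8%, Boschloo at most 5.0%. Pearson is not a safe substitute: it reaches 6.5% at 25 per arm.
- **Equal arms needed for 80% power at 60/95:** 24 with Fisher, 20 with Boschloo.

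**Step 4: the logistic option.** At a 95% return rate, the chance that every participant in the experimental arm returns is 0.95²⁵ = 0.277 at 25 per arm and 0.95¹⁹ = 0.377 at 19. The table then has an empty cell and the maximum-likelihood odds ratio is infinite. Section 9.1 does not say which logistic test (Wald, likelihood ratio or penalised) would then be used.

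**The case against.** Fisher's test is valid and conventional for small 2×2 tables. Section 9.2 names it and the Section 9.4.2 rule leads to its decision. The switch is therefore harmless, and naming Fisher alone would cure the inconsistency. With all 50 analysed 25/25, Fisher already has 82.2% power at 60/95. On this view, Boschloo is only a preference for one valid test over another. Much of that stands: Fisher is not an error, and the gain is one of efficiency.

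Four stronger readings are tempting, and the documents do not support them.

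- **That the rule always selects Fisher.** This is literally true only when an arm has fewer than 20. Near 25 per arm with no effect, Pearson is often selected. What holds is that the decision is the same.
- **That 5 to 10 points of power are lost in general.** That range fits exact arms of 25/25 and 19/19 at 60/95. Exclusions for missing outcomes and the absence of described blocking make other splits likely, and in some of them the gain is close to zero.
- **That choosing by cell count inflates the type I error.** It does not, because the rule's rejections are Fisher's.
- **That changing the test rescues the sample size.** Boschloo at 19 per arm gives 77.7%, still below 80%. At 60/90 and 60/85 the trial stays underpowered with either test (69.0% and 49.4% with Boschloo at 25/25).

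The objection does not answer the rest. Three sections still disagree, the logistic option is not workable as written, and a valid test that is never less powerful is available for a change of wording.

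**Conclusion.** The point holds as a specification fault with a cheap efficiency improvement attached; the plan's test is not invalid. The primary test should be a single rule and is currently three. At the planned size the working rule is Fisher's, with a maximum type I error of about 2.3 to 3.8% against a nominal 5%. Boschloo gains about 0 to 10 points at 60/95 depending on the arms analysed, about 4 to 7 on average over random splits, and up to about 12 at the smaller effects that Section 9.2 tabulates.

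The figures rest on 1:1 allocation, 38 to 50 analysed participants and the planned rates. The averages also assume simple randomisation.

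A separate and more serious matter remains in Section 9.2. Fisher at 19 per arm has 68.3% power, not 80%. The stated "Effect Size: Odds Ratio (OR) = 5.0" also does not match 60% versus 95%, which gives (0.95/0.05)/(0.60/0.40) = 12.7. That calculation must be restated whichever test is chosen.

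**What to change.** Before any outcome data are seen:

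1. Name the same primary test in Sections 9.1, 9.2 and 9.4.2: the two-sided Boschloo exact unconditional test at 0.05. State that tables are ordered by the two-sided Fisher p-value and that the p-value is maximised over the common return rate. The guarantee of never having less power than Fisher depends on that ordering.
2. Delete the cell-count switch in Section 9.4.2, and the logistic alternative for the primary test in Section 9.1.
3. Report Fisher's p-value as a sensitivity result.
4. Do not offer Fisher with mid-p as an equivalent. It matches Boschloo at 19 and 25 per arm, but its maximum size reaches about 5.4% at 23 per arm.
5. Restate the power in Section 9.2 for the test named.

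The cost is a few lines of text and a short enumeration, with no extra participants or visits. The one drawback is that readers know Boschloo's test less well than Fisher's, which the sensitivity result largely addresses. If the sponsor prefers Fisher for familiarity, naming it alone in all three sections would still remove the inconsistency, but the power gain would be forgone.

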 - Given the small sample size and reliance on a relatively large assumed effect size (OR = 5.0), the robustness of the sample size was tested under varying assumptions:

Control Group Return Rate (p_1)	Experimental Group Return Rate (p_2)	Effect Size (OR)	Required n per group	Total Sample Size
-------------------------------------	--	------------------	----------------------	-------------------

60%	95%	12.7	19	38
60%	90%	6.0	26	52
60%	85%	4.25	33	66

- This supports the feasibility of the current design to detect large effects, while highlighting that smaller effects will not be statistically detectable in this study.
-

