9.4 STATISTICAL ANALYSES

9.4.1 GENERAL APPROACH

- Descriptive statistics will be presented. Continuous data will be evaluated with the Shapiro-Wilk test of normality, data that is considered normal with that test will be evaluated with Levene's test of homogeneity of variances. Data that are found to be parameteric with both tests, will be treated as normally distributed and evaluated with analysis of variance (ANOVA). Continuous data that fails either test of normality listed above will be evaluated with the Mann-Whitney U. Continuous data will be presented as means \pm standard deviation, with the range. Non-parameteric continuous data will include the median as well.
- Categorical data will be evaluated with Pearson's Chi-square, or Fisher's exact test. Odds ratios will be calculated for categorical data that is found to be significantly different among the two groups.
- Statistical significance will be defined as $p < 0.05$.

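### The primary odds ratio is planned only when p<0.05, so the effect estimate is reported selectively and a non-significant result has none planned

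*Protocol*

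**What the plan says.** Protocol section 9.4.2 names return to dance, yes or no, as the primary outcome and compares the arms with Pearson's chi-square or Fisher's exact test. On the estimate it says: "Odds ratios will be calculated and presented for significant findings". Section 9.4.1 has the same rule for categorical data in general: "Odds ratios will be calculated for categorical data that is found to be significantly different among the two groups". It sets the threshold at p<0.05.

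Section 9.4.2 also says "The proportion of subjects in each group that returned to dance will be evaluated", so the arm proportions will probably be shown. Section 9.4 names no risk difference, risk ratio or confidence interval for the primary outcome, and none appears elsewhere in the protocol.

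Two other places bear on the point:
- Section 9.1 gives the primary analysis method as "Logistic regression or Fisher's exact test depending on data distribution". Section 9.4.2 does not carry logistic regression forward.
- Section 9.2 expresses the target effect as an odds ratio, "38 participants total (19 per group) to detect an OR of 5.0 with 80% power", and concludes from its sensitivity table that "smaller effects will not be statistically detectable in this study".

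**The concern.** Whether the trial's own effect measure appears depends on which side of 0.05 the p-value falls. This has two consequences.

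First, a non-significant result would be reported without an estimate and interval. In a trial this small, the interval is what separates evidence of little effect from data still compatible with a large benefit. Without it, a null result is easily read as no effect.

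Second, any odds ratio presented has been selected for being large. If the true effect is smaller than planned, the presented value tends to overstate it, and anyone pooling or citing presented odds ratios inherits that bias.

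This is a rule the protocol states in two sections. It is not a detail left open for the analysis plan, and an analysis plan that follows the protocol would inherit it.

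**Working it through.** **Inputs.** From section 9.2: two-sided alpha 0.05, power 80%, control rate 60%, app-arm rate 95%, stated OR 5.0, 19 per group required, 50 enrolled. From sections 9.4.1 and 9.4.2: OR presented if p<0.05; Fisher's test if any of the four cells is below 10. Assumed: 1:1 allocation, with 25 per arm (all 50 analysed) or 19 per arm (the stated requirement).

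**The plan's own figure.** The unpooled normal formula gives n per group = (1.960 + 0.842)² × (0.60×0.40 + 0.95×0.05) / 0.35² = 7.85 × 0.2875 / 0.1225 = 18.4, rounded up to 19, or 38 in total. The stated 38 is reproduced for 60% against 95%. Those rates correspond to OR (0.95/0.05)/(0.60/0.40) = 12.7. An OR of 5.0 from 60% means odds of 1.5 × 5 = 7.5, a rate of 7.5/8.5 = 88.2%. Both scenarios are carried below, with the 90% and 85% rows of the sensitivity table.

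**Which test decides.** Pearson's test needs all four cells to be at least 10, which is impossible with 19 per arm. With 25 per arm the most extreme such table is 10/25 vs 15/25: chi-square 2.0, p=0.157. The Pearson branch therefore never yields a presented OR, and Fisher's test alone decides.

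**Method.** Every possible 2×2 table was enumerated and weighted by its binomial probability. An OR counts as presented if two-sided Fisher p<0.05. Medians use the OR with 0.5 added to each cell, so that zero cells stay finite. Significance against the app has negligible probability in these scenarios.

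Control rate 60%; each cell gives 25 per arm / 19 per arm:

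| App-arm rate (true OR) | No OR presented | Median OR, presented results | Median OR, all results |
|---|---|---|---|
| 95% (12.7) | 18% / 32% | 13.0 / 16.7 | 11.1 / 11.2 |
| 90% (6.0) | 41% / 54% | 8.3 / 11.2 | 5.4 / 5.2 |
| 88.2% (5.0) | 49% / 61% | 7.5 / 9.1 | 4.6 / 4.7 |
| 85% (3.8) | 62% / 71% | 6.6 / 7.9 | 3.7 / 3.5 |

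With 25 per arm, the share of ORs above the true value, presented against all results, is 52% vs 43%, 77% vs 46%, 93% vs 48%, and over 99% vs 49%, in the same row order.

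**Individual results at the boundary** (control vs app, sample OR, exact conditional 95% interval):
- 15/25 vs 22/25: OR = (22×10)/(3×15) = 4.9, p=0.051, interval about 1.0 to 31. Not presented.
- 15/25 vs 23/25: OR = (23×10)/(2×15) = 7.7, p=0.018. Presented.
- 11/19 vs 17/19: OR = (17×8)/(2×11) = 6.2, p=0.062, interval 0.93 to 67. Not presented, although it exceeds the target of 5.0.
- 11/19 vs 18/19: OR = (18×8)/(1×11) = 13.1, p=0.019. Presented.

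Over all tables, the smallest sample OR favouring the app that could ever be presented is 3.8 with 25 per arm (for example 8/25 vs 16/25) and 4.8 with 19 per arm (for example 7/19 vs 14/19).

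**The case against.** **The rule does not say "only".** Neither sentence forbids an odds ratio after a non-significant result. That is literally true, but the condition is stated twice and has no purpose unless it restricts.

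**Logistic regression would give an odds ratio whatever the p-value.** It would, but section 9.1 offers it only as an alternative to Fisher's test, section 9.4.2 drops it, and nothing lifts the condition. If section 9.1 were held to prevail and logistic regression were used, an estimate would exist.

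**Interval methods belong in the analysis plan.** The choice of method and the handling of zero cells can be settled there. The significance condition cannot be left to it, because the protocol has already fixed it.

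**Little is lost in practice.** This is the strongest point, and much of it stands. With one 2×2 table and the proportions with their denominators shown, a reader can compute the odds ratio and an interval. The test, alpha and sample size are unaffected. This limits the seriousness, but it does not justify a plan that withholds its own estimate according to the p-value.

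**The percentages restate low power.** The non-reporting rates are indeed one minus the power of Fisher's test, and a significant result would show the same odds ratio after the fix. The rule's own contribution is to turn low power into a missing estimate. The largest distortions occur at 60% vs 85%, an effect that section 9.2 itself treats as beyond this trial's reach.

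**Conclusion.** The concern holds. Sections 9.4.1 and 9.4.2 make the only named between-group measure for the primary outcome conditional on p<0.05, so it is reported selectively by design.

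Under the assumptions above, the chance that no odds ratio is presented is 18% (25 per arm) to 32% (19 per arm) at the planned rates, and 49% to 61% at the stated OR of 5.0. At that OR, presented values have a median about 1.5 times the truth with 25 per arm (7.5/5.0) and 1.8 times with 19 (9.1/5.0). At the planned rates with 25 per arm the selection is small.

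The flaw lies in reporting. It does not invalidate the test or lose data. It should be corrected before analysis.

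**What to change.** Delete the significance condition in sections 9.4.1 and 9.4.2. State instead that, whatever the p-value, the primary result will be reported as both arm proportions with their denominators and the between-group effect with a 95% confidence interval. The effect should be the odds ratio, preferably with the risk difference, and the interval method should remain defined when a cell is zero.

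The cost is one sentence in each section. No extra data are needed, and the sample size, alpha and test do not change.

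### The only effect estimate named for the primary endpoint is an odds ratio, and at the plan's own 60% vs 95% it would be infinite in 33% to 51% of the significant trials that are to present it

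*Protocol*

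**What the plan says.** Section 9.4.2 compares the proportion returning to dance in each group by Pearson's chi-square or Fisher's exact test. Fisher's test is required when any of the four cells (returned or not, by group) holds fewer than 10 subjects. On the size of the effect it says only: "Odds ratios will be calculated and presented for significant findings". Section 9.4.1 has the same rule for categorical data in general. Neither section gives a confidence interval, a risk difference or a method for an empty cell.

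Section 9.1 describes the primary analysis differently: "Analysis Method: Logistic regression or Fisher"'s exact test, with the choice left to the distribution of the data. Section 9.4.2 does not mention logistic regression.

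The design assumptions are in section 9.2: "Control group: 60% expected to return to dance" and "Experimental: 95% expected to return to dance", with two-sided alpha 0.05 and 80% power. The result is "38 participants total (19 per group) to detect an OR of 5.0 with 80% power". Planned enrolment is 50. The text also gives "Effect Size: Odds Ratio (OR) = 5.0", while the robustness table in the same section shows 12.7 for 60% vs 95%.

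**The concern.** If nearly all app dancers are expected to return and each arm has about 20 people, a table with no non-returner in the app arm is an ordinary outcome. The sample odds ratio divides by that empty cell, so it has no finite value. The rule that shows the odds ratio only for significant results makes this worse, because an empty app-arm cell is nearly always a significant result. The tables in which the plan calls for an effect size are therefore those in which its chosen measure most often fails.

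At stake is whether the trial can report how much the app helped, with its uncertainty, by a method fixed in advance. Without one, the analyst must choose a substitute after seeing an unblinded result. That choice can matter a good deal, as the example under the working shows.

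**Working it through.** **Inputs.** From section 9.2: control 60%, app 95%, two-sided alpha 0.05, 80% power, 19 per group required, 50 enrolled. From section 9.4.2: Fisher's test when a cell is below 10, and the odds ratio only if significant. Assumed: 1:1 allocation (implied by 19 per group) and 19 to 25 analysed per arm. No dropout rate is stated, so the range runs from the required number to full enrolment.

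**1. The plan's own figures.** The unpooled normal approximation gives n = (1.96 + 0.8416)² × (0.60×0.40 + 0.95×0.05) / 0.35² = 18.4, so 19 per group. This matches the plan. The odds ratio for 60% vs 95% is (0.95/0.05)/(0.60/0.40) = 19/1.5 = 12.7, which matches the table and not the 5.0 in the text. An odds ratio of 5.0 from 60% means odds of 7.5, or 7.5/8.5 = 88.2%.

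**2. Chance of an empty app-arm cell.** P(every app dancer returns) = 0.95ⁿ:
- n = 19: 37.7%
- n = 22: 32.4%
- n = 25: 27.7%

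**3. Share of significant trials with an infinite odds ratio.** I enumerated all 2×2 tables with independent binomial arms and counted those with two-sided Fisher p < 0.05. At 60% vs 95%:

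| n per arm | P(significant) | P(significant and empty cell) | Infinite odds ratio among significant |
|---|---|---|---|
| 19 | 68.3% | 35.1% | 51.4% |
| 22 | 77.3% | 31.5% | 40.7% |
| 25 | 82.2% | 26.9% | 32.8% |

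The last column is the third divided by the second. A table with an empty app-arm cell is significant 93.0% of the time at n = 19 and 97.1% at n = 25.

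**4. Sensitivity to the app-arm rate** (control 60%, n = 19 to n = 25):

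| App-arm rate | P(empty cell) | Infinite odds ratio among significant |
|---|---|---|
| 95% | 37.7% to 27.7% | 51.4% to 32.8% |
| 90% | 13.5% to 7.2% | 27.4% to 11.8% |
| 88.2% (odds ratio 5.0) | 9.3% to 4.4% | 21.9% to 8.3% |
| 85% | 4.6% to 1.7% | 14.5% to 4.4% |

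**5. One table worked through: 25/25 app vs 15/25 control.**
- Fisher p = 0.0006, so the test works.
- The sample odds ratio and the conditional maximum-likelihood odds ratio are both infinite. The exact 95% interval is 3.07 to infinity.
- Adding 0.5 to each cell gives (25.5 × 10.5)/(0.5 × 15.5) = 34.5, a finite number produced by the correction and far from the design value of 12.7.
- Ordinary logistic regression does not converge. The app coefficient drifts from 10.8 (SE 54) to 31.4 (SE 1.6 million) as iterations are added.
- The risk difference is 40 percentage points, Newcombe 95% interval 19 to 59.

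**The case against.** The strongest reply is that nothing decisive breaks, and much of that reply stands. An empty cell is below 10, so 9.4.2 always sends such a table to Fisher's test, which is valid. The arm proportions are what 9.4.2 compares, so 100% vs 60% would be visible to any reader. An exact lower limit for the odds ratio also exists, although the protocol does not plan one.

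A reader might infer that a clear benefit could be reported with a p-value near 1 through the logistic option in 9.1. The documents do not support that. Logistic regression is one of two options there and is absent from 9.4.2. The bad p-value would also need a Wald test, which the protocol does not name; in the worked example the likelihood-ratio test from the same model gives chi-square 16.4, p = 0.00005. What remains is that 9.1 and 9.4.2 do not list the same methods.

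It can also be said that 95% is the most favourable of the plan's scenarios. That is fair, and the shares shrink at 90% and 85%. But the 19 per group rests on 95%, so it is the design case. At 95%, 62% to 72% of all trials still give a finite odds ratio.

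Finally, an odds ratio is a legitimate measure. That it differs from the risk ratio (12.7 against 0.95/0.60 = 1.58) calls for care in reading and is not an error. Handling of empty cells might sit in an unseen analysis plan. The protocol, however, does not leave the effect measure open: it names one, and that one often has no finite value under the protocol's own assumptions.

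**Conclusion.** The point holds for the effect estimate only. At 60% vs 95%, with 1:1 allocation and 19 to 25 analysed per arm, 38% to 28% of trials have no app-arm non-returner, and 51% to 33% of the trials required to present an odds ratio would have an infinite one. These shares depend strongly on the 95% assumption.

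It would go too far to conclude that the primary test fails, that type I error is affected or that the trial would be left with no evidence on the size of the effect. This should be fixed before data are seen, but it does not threaten the validity of the primary comparison.

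**What to change.** In 9.4.2, name the risk difference (app minus control) with a Newcombe or Miettinen-Nurminen 95% confidence interval as the primary effect measure, and report it whatever the p-value. If an odds ratio is kept, give it with an exact conditional interval or take it from Firth-penalised logistic regression.

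In 9.1, align the method with 9.4.2: delete ordinary logistic regression, or replace it with a Firth or exact version.

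The cost is a few sentences in two sections, a change in the reported effect scale and slightly more analysis work. Data collection and sample size are unchanged.
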